Fasting Blood Specimen and First Morning Urine Void Collection: Participants will transport their urine sample to study office for collection. Trained staff will collect and record the urine specimen intake (Attachment 14). The blood collection procedure consists of administering and recording responses to a blood draw screening questionnaire for conditions that exclude the participant from the blood draw (hemophilia, skin condition, or chemotherapy in the past four weeks, and pregnancy), ask about having diabetes, taking blood thinning medications, participant's weight, and fasting status (Attachment 14). Next, phlebotomists will draw 23-ml (0.8 ounces or about 5 teaspoons) of blood from the child participant and 33-ml (1.1 ounces or about 7 teaspoons) of blood from the adult participant using standard venipuncture techniques (Attachment 12) and record the outcome (Attachment 14). If a person is unable to provide the desired volume of blood, a smaller amount can be drawn and documented. Trained study staff will record the phlebotomy and urine collection result on the Blood Draw and Urine Collection Form (Attachment 14).

Common adverse events from blood draws include bruising, bleeding, and fainting. No serious adverse events are anticipated in drawing these volumes of blood. Fasting diabetic participants who use insulin will receive priority appointments for their blood draw. Light snacks will be provided following blood collection. While each participant will be asked to provide a fasting sample, it is recognized that some may not be able to fast. Variations in lipids levels due to fasting will affect PFAS compounds measurements to a lesser extent as PFAS in serum are bound to proteins not the lipid fraction. . In the C8 Science Panel studies, about 25% of participants fasted – but they were not asked to do so (Frisbee 2009).

Phlebotomists will extract serum, and label and prepare the serum and urine specimens for secure storage
 and transport from the study office to the CDC NCEH laboratory in Atlanta, GA (Attachment 12).

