Attachment 7a. Appointment Reminder Card and Instructions

Multi-site PFAS Health Study Appointment Reminder Card

Clinic Visit

	Appointment Information for Your Multi-site Study Interview
	[NAME OF LOCATION]
	[Street Address]
	[Local or Toll Free Telephone Number]
	Day:
	Date: ////
	Time: : AM PM
	Study ID No.:
	Please bring this paper with you.
We will draw a blo	od sample so please do not eat for at least 8 hours before your appointment. You may drink water during this time.
Don't forget to c	ollect your urine sample in the morning. Bring your urine sample with you.
	If you take diabetic medication, see special instructions. Don't forget to bring all your medication for us to see.
[If you ar	e a past participant in the [insert site] PFAS Blood Testing Program, please bring a copy of your results report.]
	If you are unable to keep this appointment, please call to set up another time.
	Toll-free (xxx)xxx-xxxx

Multi-site PFAS Study Appointment Reminder Card

Home Visit				
Appointment Information for Your Multi-site PFAS Study Interview				
We will arrive at your home on the date and time below:				
Day:				
Date: / /				
Time: : 🗆 AM 🗆 PM				
Study ID No.:				
We will draw a blood sample so please do not eat for at least 8 hours before your appointment. You may drink water during this time.				
Don't forget to collect your urine sample in the morning.				
If you take diabetic medication, see special instructions. Don't forget to gather all your medication for us to see.				
[If you are a past participant in the [insert site] PFAS Blood Testing Program, please provide a copy of your results report.]				
If you are unable to keep this appointment, please call to set up another time.				
Toll-free (xxx)xxx-xxxx				

Multi-site Study Appointment Reminder Card – Instructions

Instructions for Study Participants

On the day of your appointment

Fasting: Do not eat or drink for at least 8 hours before your appointment. Do not have candy, gum, or soda. Drinking water is fine. Take all your medications with water only.

If you have diabetes and take insulin or other medications, we will schedule your appointment as early in the morning as possible. Please fast for at least 8 hours if your meal and medication plan allows. If you must eat before your appointment, please eat fat-free or low-fat items and take your medications as usual. Write down what you ate and when you ate it.

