8. Tell me the last time you ate. Was it less than	n eight hours ago?	🗆 Yes 🗌 No
8a. [IF YES] How long ago did you eat?	: (hours and minutes)	
8b and what did you eat?	I	
[IF THE PARTICIPANT ANSWERED 'YES' TO ANY COORDINATOR AND SUPERVISING NURSE TO M	OF THE ABOVE QUESTIONS PLEASE SEE S IAKE SURE THEY CAN SAFELY PROVIDE BI	TUDY LOOD SAMPLE]
9. Result of the Blood Draw (mark one)	Volume	
□ Complete	(35-mL adults/25 ml children)	
Partial	7a. (mL)	
Unable to collect		
9a. Date: _ / / 9b. Tin	ne: _ : 🗆 AM 🗆 PM	
9c. Code Partial/Inability to Collect (circle one)		
Reason for partial or inability to collect blood:		
 Pregnant Medical (e.g. patient frail, weak, lost consciousness) Refused 		
4. Other (describe)		

NOTES: Care should be used in drawing blood from all subjects. Common adverse effects include bruising, bleeding, and fainting. Please ask all participants whether they prefer to lie down to have blood drawn.

Ask everyone if they tend to faint when giving blood. Suggest they sit down for five minutes after giving blood.

Fasting diabetic participants who use insulin will be given priority appointments for their blood draw.

Light snacks will be provided following blood collection.

See Protocol Attachment 14 (Manual of Operations) for further details on collecting blood samples.

[ON INVESTIGATORS INSTITUTION LETTERHEAD] [DATE]

[NAME OF PROVIDER] [ADDRESS] [CITY, STATE ZIP CODE]

Subject: Medical verification and records review for Multi-site PFAS Health Study

Dear [NAME OF PROVIDER]:

The Agency for Toxic Substances and Disease Registry (ATSDR) and [insert institution name] are conducting a research study of the health effects from exposure to per- and polyfluoroalkyl substances (PFAS) found in drinking water. We are working with the assistance of your local health department [insert name] and [name of all other partners]. ATSDR and research partners are conducting this research study with oversight from the CDC/ATSDR Institutional Review Board (IRB) under CDC Protocol No. xxxxxxx.

Under Section 8006 of the 2018 Consolidated Appropriations Act, Congress authorized ATSDR to study the impact that exposure to PFAS in drinking water might have on the health of affected citizens. This study will see if there is an increase of symptoms or illness related to these chemicals.

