Attachment 20b. Letter Report of Critical Values

If you or your doctor has a question about these test results, please call us at [insert telephone number].

Thank you for [your/your child's] participation in the study.

[name], PhD Co-Principal Investigators Pease Study [name], DSc

Multi-site Study Clinical Test Results Report

Dear [NAME/NAME OF PARENT OR GUARDIAN],

The following tables show the results of clinical tests that we performed in [your/your child's] blood or serum on $|_|_|/|_||/|_|||||$. The results that are out of normal range are marked red.

These clinical tests are mostly those that your doctor would perform in an office. We advise you to go over the results with your doctor. If he or she has any questions about some of the more specialized tests we did, he or she can contact us at the number provided below.

Because we are providing these results |__| months after ATSDR and [insert institution name] collected [your/your child's] blood, the results may be of limited value to you or your doctor, especially if you are already under treatment or being followed for a particular chronic condition that the results indicate.

Some people will not have results for all chemicals. [You/Your child] may not have a result for a chemical test if [your/his/her] level is lower than the lab's limit of detection (<LOD). [You/Your child] may also not have a result if the blood sample did not pass a lab quality control check. If the reason for missing results is known, it will be included with [your/your child's] results.

You or your physician may contact us with questions about [your/your child's] clinical test results by calling ATSDR at [study telephone number].

Thank you for your understanding and your participation in the study.

Sincerely,

Study Investigators

Attachment 21

Table 1. Results of your clinical tests for thyroid hormones, glycemic parameters, lipids, and liver function.

* NOTE: the displayed clinical ranges will be updated when the contract labs are selected.

Test name	Your Result	Adult Comparison Values	Child Comparison Values
Thyroid Hormones and Antibodies		Clinical Ranges	
Thuroid Stimulating Hormono (TSH)		18-19 years: 0.5-4.3 mIU/L ¹	4-5 years: 0.7-6.0 mIU/L
Thyroid Stillidating Hormone (1311)		>20 years: 0.3-4.2 mIU/L	6-10 years: 0.6-4.8 mIU/L
		18 -19 years: 5.9-13.2 mcg/dL ²	
		≥20 years): 4.5-11.7 mcg/dL	4-5 years: 6.0-14.7 mcg/dL
Total Thyroxin (TT4)			6 -10 years: 6.0-13.8 mcg/dL

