	81-85 years: 34-177 ng/mL	
	86-90 years: 33-175 ng/mL	
	≥91 years: 25-179 ng/mL	
Glycemic Parameters	Clinical Guidelines and Ranges	
	Normal: <100 mg/dL ¹⁰	
	Prediabetes: 100–125 mg/dL	
Glucose, fasting, 8-hr	Diabetes: ≥126 mg/dL	
	Critical Value: <40 mg/dL ¹¹	
	Critical Value: ≥400 mg/dL ¹⁰	
Insulin	<17 µU/ml ³	
	Diabetes Risk ¹²	
Glycosylated Hemoglobin (HbA1c)	Normal: <5.7%	Criteria for diagnosing diabetes have
Giveosylated Hemoglobin (HDATC)	Prediabetes: 5.7-6.4%	not been established
	Diabetes: ≥6.5%	not been established.
Thyrosine Phosphatase-like Protein Autoantibodies	Negative Antibody: DK<5 ³	Store for later
(IA 2)	Positive Antibody: DK≥5	
Glutamate Decarboxylase -65 (anti-GAD 65)	Negative Antibody: DK≤33 ³	Store for later
Giulamale Decarboxylase -65 (anti-GAD 65)	Positive Antibody: DK>33	

 ¹⁰ http://www.diabetes.org/diabetes-basics/diagnosis/?loc=db-slabnav
 https://www.mayomedicallaboratories.com/test-catalog/appendix/criticalvalues/view.php?name=Critical+Values%2FCritical+Results+List
 https://www.mayomedicallaboratories.com/test-catalog/Clinical+and+Interpretive/82080
Attachment 21

Linids	Clinical Guidelines and Panges	
	Coronany Upart Disease Bisk (CUD) ¹³	
	Coronary Heart Disease Risk (CHD)	
Total Cholesterol, fasting	Adult, 18+ years:	Child, 2-17 years:
	Desirable: <200 mg/dL	Acceptable: <170 mg/dL
	Borderline High: 200-239 mg/dL	Borderline high: 170-199 mg/dL
	High: ≥240 mg/dL	High: ≥200 mg/dL
	CHD Risk ¹²	
	Adult, 18+ years:	Child, 2-9 years:
	Normal: <150 mg/dL	Acceptable: <75 mg/dL
	Borderline High: 150-199 mg/dL	Borderline high: 75-99 mg/dL
	High: 200-499 mg/dL	High: ≥100 mg/dL
Triglycerides, fasting	Very High: ≥500 mg/dL	
	, c c.	Child, 10-17 years:
	Critical Value: >1.000 mg/dL	Acceptable: <90 mg/dL
	,	Borderline high: 90-129 mg/dl
		High: $>$ or =130 mg/dl
	CHD Risk ¹²	
	Adult 18+ years:	Child 2-17 years:
Low Density Lineprotein Cholectorel (LDL) fasting	Desirable: <100 mg/dl	Accontable: $<110 \text{ mg/dl}$
	Above Desirable: 100 120 mg/dl	Rorderline high: 110 120 mg/dl
Low Density Lipoprotein Cholesteror (LDL), fasting	Above Desilable. 100-129 mg/dL	Llight >120 mg/dl
	Bordenine night 130-159 mg/dL	High: 2130 Hig/dL
	Very nign: ≥190 mg/dL	
	CHD Risk¹²	
	Adult, 18+ years:	Child, 2-17 years:
High Density Lipoprotein Cholesterol (HDL), fasting	Males: ≥40 mg/dL	Low: <40 mg/dL
	Females: ≥50 mg/dL	Borderline low: 40-45 mg/dL
		Acceptable: > 45 mg/dL
VLDL		
Liver Tests	Clinical Ranges	

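### Non-fasting samples are accepted for a reason that concerns PFAS only, yet the results reports label glucose and lipids as fasting and ignore the recorded fasting status

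*Protocol*

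**What the plan says.** Section 3.6.4 concedes that "While each participant will be asked to provide a fasting sample, it is recognized that some may not be able to fast". Its scientific reason for accepting such samples is that "Variations in lipids levels due to fasting will affect PFAS compounds measurements to a lesser extent as PFAS in serum are bound to proteins". It adds that in the C8 studies "about 25% of participants fasted – but they were not asked to do so". It says nothing about how eating affects glucose, insulin or triglycerides, all of which are hypothesis endpoints for children and adults (section 2.5.2).

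Sections 3.7.1 and 3.7.2 describe the whole list of effect biomarkers as measured in fasting serum, without exception. Attachment 2 likewise lists the lipids as fasting and glucose as an 8-hour fasting value.

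Participants are told to fast for at least 8 hours. People on diabetes medication are asked to fast if they can. Those who cannot are told in Attachment 7a: "If you must eat before your appointment, please eat fat-free or low-fat items and take your medications as usual". The reminder call (Attachment 8) says much the same.

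On the Blood Draw and Urine Collection Form (Attachment 14), item 8 begins "Tell me the last time you ate. Was it less than" and completes the question with eight hours. Item 8a asks "How long ago did you eat", and item 8b asks what was eaten.

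The clinical results report (Attachment 21) has a row headed "Glucose, fasting, 8-hr" and labels total cholesterol, triglycerides, LDL and HDL as fasting. Its covering text states: "The results that are out of normal range are marked red". The critical-value letter (Attachment 20b) also labels its glucose row as fasting.

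**The concern.** The justification protects the exposure measurement and leaves the outcome measurements uncovered. The study may hold a record that a person ate two hours before the draw and still send that person a report calling the glucose value an 8-hour fasting result, placed in a diabetes-risk band and possibly printed in red. Section 2.6 says participants can use their results for medical decisions, so the label matters.

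The bands are narrow. Glucose passes from the top of normal (100 mg/dL) to the diabetes band (126 mg/dL) over 26 mg/dL. Triglycerides at ages 2–9 pass from the top of acceptable (75) to high (100) over 25 mg/dL.

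In the analysis, values described as fasting would include some that are not. Non-fasting may also be selective, because the instructions allow eating only for people on diabetes medication, and diabetes is itself a hypothesised outcome.

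**Working it through.** The protocol gives no figure on this point. The main check is to set its parts side by side; the arithmetic after that only gives scale.

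**Text check**

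1. *Reason against scope.* The reason in 3.6.4 concerns PFAS binding to protein. The wording in 3.7.1, 3.7.2 and Attachment 2 concerns lipids, glucose and the other effect biomarkers. The reason does not reach them, and fasting serum without exception cannot be squared with accepting people who have eaten.
2. *What is recorded.* Attachment 14 captures fasting under 8 hours, hours and minutes since eating, and the food.
3. *What happens to the record.* The only use printed on the form is to refer a yes answer to the coordinator and supervising nurse for a safety check. Section 3.8.4 names questionnaire, medical and school record and laboratory data, a shipping log and body measures. It provides for double entry from paper forms generally but does not name the fasting items.
4. *What is reported.* Attachment 21 explains missing results, detection limits, quality-control failures and delay. It has no field or caveat for fasting. Glucose has one set of bands (below 100, 100–125, 126 and above). Triglycerides have three age-specific sets: four bands for adults, and three each for ages 2–9 and 10–17.
5. *Critical-value letter.* Attachment 20b uses only glucose below 40 or above 400 mg/dL. Its fasting label can be wrong, but it does not apply the 100 and 126 bands.

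**Inputs for scale.** From the documents: 6,000 adults, 2,000 children, two-sided alpha .05, power .80, and quartiles, so 6,000 / 4 = 1,500 adults per quartile. Assumed, because the documents give no figure: share not fasting *q*; food effect *s* of 0.25–1 SD; normal values; a cut-off 1–2 SD above the mean; and a difference in non-fasting between exposure groups *Δq* of 2–20 percentage points.

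**The protocol's formula reproduced.** With equal groups, n = 2·SD²·(1.96 + 0.8416)²/Δ², where 2.8016² = 7.849.
- Child total cholesterol: 2 × 29.3² × 7.849 / 4.6² gives 637; with a difference of 9.3 it gives 156.
- Adult total cholesterol: 2 × 41.9² × 7.849 / 11² gives 228.

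All three match Tables 1 and 2. The same formula with 1,500 per quartile gives a detectable difference of 2.8016 × √(2/1,500) = 0.102 SD.

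**Wrong labels.** Each 10% not fasting is 0.10 × 6,000 = 600 adults and 0.10 × 2,000 = 200 children. If 5–30% did not fast, that is 0.05 × 8,000 = 400 to 0.30 × 8,000 = 2,400 people.

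**Wrong categories.** The extra share labelled high among people who ate is [1 − Φ(c − s)] − [1 − Φ(c)].
- With c = 1.5, 6.7% would be above the cut-off when fasting, against 10.6% (s = 0.25) to 30.8% (s = 1) after eating. The extra share is 0.0388 to 0.2417.
- Among 6,000 adults with q = 5%: 300 × 0.0388 to 300 × 0.2417, about 12 to 73 people. With q = 25%: about 58 to 363.
- Letting c run from 2 to 1 widens these to 5–102 and 26–512.

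**Precision if fasting is ignored.** The variance grows by 1 + q(1 − q)s². At the 0.102 SD difference, with s = 0.5, power is 79.5% at q = 5% and 78.2% at q = 25%. With s = 1 and q = 25% the variance factor is 1.1875 and power is 72.9%.

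**Bias if fasting is ignored.** Bias in the group difference is Δq × s. It is zero when Δq is zero. A 5-point difference gives 0.05 × 0.25 = 0.0125 to 0.05 × 1 = 0.05 SD; a 20-point difference gives 0.05 to 0.20 SD.

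**The case against.** The strongest reply is that the protocol asks everyone to fast, repeats the request in the reminder call and records departures in detail. Adjustment, restriction or a sensitivity analysis is therefore possible, and the choice may sit in an analysis plan that was not available. This stands. A reader might infer that the glucose, insulin and triglyceride outcomes are contaminated; the documents do not show that. Comparisons are made across PFAS levels, and nothing indicates that non-fasting varies with them.

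A reader might also infer that people who ate will be wrongly told they have diabetes. That too goes beyond the documents. Not everyone who ate crosses a cut-off, and those expressly allowed to eat are already treated for diabetes. The questionnaire's diabetes item rests on self-report with attempted record confirmation (section 3.6.5.2), and HbA1c is measured and reported alongside glucose. The report advises going over results with a doctor, and its ranges are provisional until laboratories are chosen.

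None of this answers the narrower point. The report template states a fasting condition that the study's own form may show to be untrue, and an analysis plan would not ordinarily correct a participant letter.

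**Conclusion.** The inconsistency is real and lies in the protocol's own text and templates. Section 3.6.4 accepts non-fasting samples for a reason limited to PFAS. Sections 3.7.1 and 3.7.2 call all specimens fasting. Attachments 20b and 21 print fasting labels, and Attachment 21 also applies fasting bands and red marking, without using the status recorded in Attachment 14. Participants who ate may receive a wrong fasting label or category.

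The number is unknown. The 400–2,400 range rests on an assumed 5–30% and counts everyone who ate, not everyone reclassified. The category counts rest on assumed food effects and cut-off positions. The C8 rate says little here, because that cohort was not asked to fast. Ignoring fasting costs little power at moderate assumed food effects, and more at a 1 SD effect. Bias requires non-fasting to differ by PFAS level; that is possible if PFAS is related to diabetes treatment, but the documents do not establish it.

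**What to change.** - Reconcile section 3.6.4 with sections 3.7.1 and 3.7.2, Attachment 2, and Attachments 20b and 21: say that fasting is requested, that some samples will not be fasting, and that the PFAS argument does not extend to the effect biomarkers.
- Name Attachment 14 items 8 and 8a as variables to be carried into the laboratory dataset (section 3.8.4).
- In Attachments 20b and 21, print fasting status and hours since the last meal. Where item 8 shows less than 8 hours, do not present the value as fasting or assign it a fasting category.
- For glucose, insulin, triglycerides and LDL, keep all samples in the main analysis with recorded fasting status or hours since the meal as a covariate, and use the fasting-only subset as a sensitivity analysis. Restricting the main analysis to fasting samples is tempting, but it would selectively drop people treated for diabetes. If an analysis plan already settles this, a cross-reference is enough.

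The cost is one added dataset variable, which is already collected on paper, a line in two report templates and a few sentences of protocol text.
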